18.4. ECG EVALUATIONS

Results from the central ECG data will be included in the reporting of this study. The following ECG parameters will be reported for this study:

- PR Interval (msec)
- QRS Interval (msec)
- QT Interval (msec)
- QTcB Interval (msec)
- QTcF Interval (msec)
- Heart rate (HR) (beats per minute [bpm])
- RR interval (msec)
- Derived HR (msec), calculated as $60000/RR$ interval [for data checking only: should be within 5% of HR]
- Overall evaluation of ECG:
 - Normal
 - Abnormal (not Clinically Significant)

Document: T:\sas\Debiopharm\Debio_1143\CZA60507\Biostatistics\Documentation\SAP\SAP Text\V5

Author: XXXXXXXXXX Version Number: 5.0
Version Date: 19APR2022

Template No.: CS_TP_BS016 Revision 5
Effective Date: 01Apr2018

Reference: CS_WI_BS005

Copyright © 2009, 2010, 2012, 2016, 2018 IQVIA. All rights reserved. The contents of this document are confidential and proprietary to IQVIA Holdings Inc. and its subsidiaries. Unauthorized use, disclosure or reproduction is strictly prohibited.

- Abnormal, Clinically Significant (ACS)

The mean of the triplicate values will be used for descriptive statistics.

The following summaries will be provided for ECG data:

- Actual and change from baseline by visit (for quantitative measurements)
- Shift from baseline according to markedly abnormal criteria for absolute quantitative measurements
- Listing of all ECG assessment results flagging markedly abnormal criteria (displaying both individual measurements and mean of the triplicates)

18.4.1. ECG MARKEDLY ABNORMAL CRITERIA

Markedly abnormal quantitative ECG measurements will be identified in accordance with the following predefined markedly abnormal criteria:

- Absolute values for QRS interval will be classified as:
 - < 50 msec
 - > 110 msec
- Absolute values for QT interval, QTcB interval and QTcF interval will be classified as:
 - > 450 msec
 - > 480 msec
 - > 500 msec
- Change from baseline for QTcB interval, and QTcF interval will be classified as:
 - >30 msec increase from baseline
 - >60 msec increase from baseline

For the markedly abnormal criteria summary, each individual triplicate should be use.

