### 9.1.6. Adverse events of special interest

AESIs are

1. for Debio 1143:
  - a. AST or ALT increases >3 ULN associated with total bilirubin >2 ULN and ALP <2 ULN
  - b. Lipase or amylase increases >5 ULN
  - c. Any QTcF prolongation above 30 ms compared to baseline on at least two consecutive readings or other ECG abnormalities such as Torsade de Pointe, ventricular tachycardia, ventricular fibrillation, flutter or any other new cardiac abnormality at the ECG or during the physical examination considered as clinically significant.
2. for nivolumab:
  - a. Any AEs that are suspected to be immune-related or infusion-related including drug hypersensitivity, immune-related pneumonitis, immune-related colitis, immune-related hepatitis, immune-related endocrinopathies such as: thyroid disorders, adrenal insufficiency, new onset type I diabetes mellitus, pituitary disorders; or immune-related

nephritis and renal dysfunction and other immune-related AEs such as: myositis, myocarditis, Guillain-Barré syndrome or uveitis of any grade

All AESIs, occurring after treatment start on C1D1 must be reported to the sponsor in the appropriate eCRF pages. When reporting these cases, it has to be specified in the eCRF whether the case is serious or non-serious. If the AESI(s) is/are serious or considered to be a DLT, then it has to be properly reported within 24 hours of acknowledgement and all applicable SAEs reporting guidelines should be followed (as described in [section 9.2](#)) including the reason why it is considered serious.

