##### Vital signs

Vital signs at each timepoint will be presented as descriptive statistics. Shift tables from baseline to the worst on-treatment values will be provided by dose level using category defined below. The worst on-treatment value is defined as the most extreme change from baseline, i.e. the maximum absolute change from baseline. The limits for defining the three shift categories refer to the magnitude of the change from pre-treatment to worst case. For blood pressure (BP), the three categories are defined as: “Change to Low” (decrease from pre-treatment >20 mmHg), “No change” (change from pre-treatment within ± 20 mmHg) and “Change to High” (increase from pre-treatment >20 mmHg). The limit for pulse rate is set to 20 beats per minute (bpm). Scatter plots will be produced, presenting the highest and lowest on-treatment results in separate figures for each vital signs.

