## ECG

Digital High-Quality ECG will be obtained by triplicate at pre-treatment, on-treatment, and change from pre-treatment to on-treatment will be analyzed centrally and will be presented as descriptive statistics, as appropriate. The number and percentage of patients with significant QTcF prolongation will be reported as contingency tables. Significant QTcF prolongation is defined as an interval >500 ms or an interval which increases by 60 ms over baseline. Several QTc prolongation analyses using different categories limits (>450, >480 and >500 ms, as well as increases from baseline of >30 ms and >60 ms) will be performed as per ICH-E14 guidelines.

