18.5.1. VITAL SIGNS MARKEDLY ABNORMAL CRITERIA

Markedly abnormal quantitative vital signs measurements will be identified in accordance with the following predefined markedly abnormal criteria:

Variable	Unit	Low	High
Weight	kg	Percentage change from baseline \leq -20%	None
SBP	mmHg	\leq 90 mmHg OR change from baseline \leq -20 mmHg	\geq 140 mmHg OR change from baseline \geq 20 mmHg
DBP	mmHg	\leq 60 mmHg OR change from baseline \leq -20 mmHg	\geq 90 mmHg OR change from baseline \geq 20 mmHg
Heart rate	Bpm	\leq 50 bpm OR change from baseline \leq -20 bpm	\geq 100 bpm OR change from baseline \geq 20 bpm

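### SAP 18.5.1 replaces the protocol's change-only vital-sign categories without declaring it, and SAP 18.4.1 counts QTc outliers on single readings although SAP 18.4 averages the triplicate

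*SAP*

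**What the plan says.** **Vital signs.** The Vital signs paragraph of protocol 11.6.4.4 sets up three categories, Change to Low, No change and Change to High, and states: "The limits for defining the three shift categories refer to the magnitude of the change from pre-treatment to worst case". The blood-pressure limit is more than 20 mmHg in either direction, and the pulse limit is 20 bpm. The worst value is the one with the largest absolute change, so each patient falls in one category. SAP 18.5.1 uses a different rule, with limits of the form "mmHg OR change from baseline": systolic ≤90 or a fall of 20 or more is Low, and ≥140 or a rise of 20 or more is High. Diastolic pressure (60/90 mmHg) and heart rate (50/100 bpm) follow the same pattern. SAP 18.5 builds its shift table on these criteria. SAP 4.3, the list of changes from the protocol, does not mention them.

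**ECG.** SAP 18.4 states: "The mean of the triplicate values will be used for descriptive statistics". SAP 18.4.1 then states: "For the markedly abnormal criteria summary, each individual triplicate should be use". The SAP listing covers both, "displaying both individual measurements and mean of the triplicates". The ECG paragraph of protocol 11.6.4.4 gives the cut-offs (">450, >480 and >500 ms, as well as increases from baseline of >30 ms and >60 ms") but does not say whether they apply to the mean or to single readings. The protocol's adverse event of special interest is worded: "Any QTcF prolongation above 30 ms compared to baseline on at least two consecutive readings".

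**The concern.** SAP 4.3 records changes as small as PK plot scales. A reader comparing the report with the protocol would therefore expect the vital-sign shift table to hold the protocol's categories. It will not, and no other output in SAP 18.5 supplies them. Changes in vital signs are a named secondary endpoint, and the study has no control arm to show how many patients a rule flags through ordinary variation.

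On the ECG side, the triplicate exists so that reading noise can be averaged out. The descriptive tables do this and the category counts do not, so the two sets of QTc results in one report rest on different units. More readings per patient also give noise more chances to cross a limit.

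**Working it through.** **1. What the two vital-sign rules do to the same readings** (illustrative systolic values, no assumption needed)

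| Baseline → on treatment | Change | Protocol | SAP 18.5.1 |
|---|---|---|---|
| 138 → 141 | +3 | No change | High (≥140) |
| 115 → 135 | +20 | No change (not >20) | High (≥20) |
| 165 → 143 | −22 | Low | Low (≤−20) and High (≥140) |

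The last row shows that one reading can meet both SAP definitions. For laboratory parameters SAP 18.3 has a combined low-and-high class; 18.5.1 has none.

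**2. Size, vital signs.** The documents state no flag rate and no SDs, so there is no figure to reproduce and all means and SDs below are assumed. There is no treatment effect, and a patient counts if any post-baseline value meets the rule. The schedule in protocol 8.2.2.2 gives a patient treated for three cycles 3 + 2 + 2 visits plus end of treatment, so 8 post-baseline visits.

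Systolic pressure, mean 125, between-patient SD 15, within-patient SD 9:
- At or above 140 at baseline: total SD √(15² + 9²) = 17.5; (140 − 125)/17.5 = 0.86; about 20%.
- Change above 20 at one visit: SD of change 9√2 = 12.7; 20/12.7 = 1.57; 5.8%. Over 8 visits sharing one baseline, simulation gives about 25%.
- SAP High over 8 visits, simulated: about 56%. Counting only patients below 140 at baseline: about 38% of all patients.
- Both Low and High under the SAP: about 13%.

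A second set (SBP mean 125, SD 14; DBP 75, 9; heart rate 80, 11; values in whole units; 8 visits) gives the share with any flag, Low or High:

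| | Within-patient SD | SAP | Protocol | Difference (points) | Range of SDs: SAP vs protocol |
|---|---|---|---|---|---|
| SBP | 8 | 65.3% | 33.0% | 32.3 | 6–12: 44–91% vs 9–76% |
| DBP | 7 | 69.6% | 20.1% | 49.5 | 5–9: 45–87% vs 2.5–46% |
| Heart rate | 8 | 54.9% | 33.1% | 21.8 | 6–10: 30–75% vs 9–58% |

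Counting only patients whose baseline was not already in the same absolute category, the SAP shares at these SDs are 54%, 58% and 51%. With a single post-baseline visit, SBP is 20–42% under the SAP and 1.5–23% under the protocol.

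**3. Size, ECG.** Protocol 8.2.2.4 schedules 5 days × 3 time points = 15. Less the pre-dose point on Cycle 1 Day 1, that leaves 14 post-dose time points, or 14 × 3 = 42 single readings for a patient who reaches Cycle 3. The baseline is the mean of the pre-dose triplicate. Assumed SDs are 8 ms between time points and 8 ms between replicates:
- SD of a single-reading change: √(8² + 8² + 8² + 8²/3) = 14.6; 30/14.6 = 2.05; 2.0% per reading.
- SD of a mean change: √(8² + 8²/3 + 8² + 8²/3) = 13.1; 30/13.1 = 2.30; 1.1% per time point.

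Over the whole schedule, with mean QTcF 415 and between-patient SD 18 also assumed:

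| Category | Triplicate mean | Single reading | Range, mean vs single |
|---|---|---|---|
| >30 ms increase | 9% | 29% | 1–22% vs 4–49% |
| >450 ms | 15% | 28% | 9–23% vs 14–47% |
| >480 ms | 0.4% | 1.5% | 0.2–1% vs 0.3–5% |
| >500 ms | about 0 | about 0 | ≤0.1% vs ≤0.5% |
| >60 ms increase | about 0 | about 0 | ≤0.3% vs 0–3.5% |

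The >30 ms range uses time-point SDs of 6–10 and replicate SDs of 5–10 ms. The other ranges use replicate SDs of 4–12 ms; over that span >30 ms runs 0.5–25% against 2–59%.

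**The case against.** The strongest reply is that little is lost. Protocol 11.6 leaves the definitive analysis to the SAP. The secondary endpoint is worded as changes in vital signs, without categories, and SAP 18.5 still reports values and changes by visit, box plots and scatter plots. The table is a shift from baseline, so a patient at 140 or more both times shows as High to High. The protocol's own rule also flags many unchanged patients. All of this stands. It limits the size of the point but does not supply the protocol's categories or the missing entry in SAP 4.3.

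On ECG, screening single readings is a defensible, sensitive choice, and no protocol rule forbids it. The adverse event of special interest is reported by the investigator on the eCRF and is not this table. The shift table named in SAP 18.4 is limited ("Shift from baseline according to markedly abnormal criteria for absolute quantitative measurements"), so it is unclear whether the >30 and >60 ms counts are tabulated at all or only flagged in the listing. Neither 18.4 nor 18.4.1 states a worst-value rule, so taking the maximum over 42 readings is an interpretation. These points also stand, and they make the ECG part the smaller one.

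**Conclusion.** The vital-sign departure is certain from the text: different criteria, ≥20 in place of >20, categories that are no longer exclusive, and no entry in SAP 4.3. Its size depends on assumed means, SDs and visit numbers. The relevant quantity is the excess over the protocol rule, about 22 to 50 points across the three measures at mid-range SDs. For systolic High it is 56% against 25%, or 38% against 25% once patients already at or above 140 are left out of the SAP count.

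The ECG point is an inconsistency inside the SAP. It matters mainly for >30 ms and >450 ms. It is small for >480 ms and near zero for >500 ms and >60 ms at moderate noise. The protocol's own definition of significant prolongation rests on those last two limits.

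A reader might infer more: that the ECG rule breaches the protocol, that large shares of patients will be flagged with nothing changed, or that noise would hide a real QT effect. The documents do not support these readings. The protocol is silent on mean or single reading. The shares rest on assumed SDs, and the outputs are shifts from baseline. QTcF changes by visit are still summarised on triplicate means, SAP 19.3 plans regressions of QTcF on exposure, and nothing names the outlier share as the main ECG result.

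**What to change.** - **SAP 18.5.1:** tabulate the protocol's three categories, using the largest absolute change and a limit of more than 20. If the absolute limits are wanted, put them in a separate table. Record any remaining departure in SAP 4.3. Joining the two limits with AND would not restore the protocol's rule: a rise from 110 to 135 mmHg (+25) would be lost because it stays below 140.
- **SAP 18.4.1:** base the QTc category counts on the triplicate mean at each time point, against the mean of the pre-dose triplicate (SAP 7.2 does not say which baseline value is meant). State whether the >30 and >60 ms categories are tabulated. Keep single readings in the listing already planned.

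The cost is SAP wording and table programming, with no new data. The downside is that an isolated high single ECG reading would appear only in the listing.

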18.5. VITAL SIGNS

The following vital sign measurements will be reported for this study:

- Systolic Blood Pressure (mmHg)
- Diastolic Blood Pressure (mmHg)
- Heart Rate (bpm)
- Temperature (⁰C)

Document: T:\sas\Debiopharm\Debio_1143\CZA60507\Biostatistics\Documentation\SAP\SAP Text\V5

Author: ██████████

Version Number:

5.0

Version Date:

19APR2022

Template No.: CS_TP_BS016 Revision 5

Reference: CS_WI_BS005

Effective Date: 01Apr2018

Copyright © 2009, 2010, 2012, 2016, 2018 IQVIA. All rights reserved. The contents of this document are confidential and proprietary to IQVIA Holdings Inc. and its subsidiaries. Unauthorized use, disclosure or reproduction is strictly prohibited.

- Weight (kg)

The following summaries will be provided for vital signs data:

- Actual and change from baseline by visit
- Shift from baseline according to markedly abnormal criteria
- Listing of all vital signs assessment results flagging markedly abnormal criteria
- Box plots of actual values and change from baseline over time:
 - At least 3 cycles will be displayed
 - For part A, a separate plot will be produced for each dose level and then overall
 - For part B, one plot indicating the patients' cohort will be produced
- Scatter plots showing pre-treatment vs. lowest/highest on-treatment levels for each vital signs parameter.

18.5.1. VITAL SIGNS MARKEDLY ABNORMAL CRITERIA

Markedly abnormal quantitative vital signs measurements will be identified in accordance with the following predefined markedly abnormal criteria:

Variable	Unit	Low	High
Weight	kg	Percentage change from baseline \leq -20%	None
SBP	mmHg	\leq 90 mmHg OR change from baseline \leq -20 mmHg	\geq 140 mmHg OR change from baseline \geq 20 mmHg
DBP	mmHg	\leq 60 mmHg OR change from baseline \leq -20 mmHg	\geq 90 mmHg OR change from baseline \geq 20 mmHg
Heart rate	Bpm	\leq 50 bpm OR change from baseline \leq -20 bpm	\geq 100 bpm OR change from baseline \geq 20 bpm

18.6. ECOG-PS

ECOG-PS will be presented as contingency tables by assessment timepoint. In addition, a shift table showing worst (higher score) on-treatment result will be presented. All ECOG-PS results will also be included in a listing.

19. PHARMACOKINETICS

Pharmacokinetics analysis will be performed on safety analysis set. Rather than excluding patients and create PK analysis set, some PK data may be excluded as not valid due to protocol violations/deviations or events with potential to significantly affect the concentration data (examples include, but may not be limited to, sample processing errors that lead to inaccurate bioanalytical results, time windows or concomitant use of prohibited medications). Unscheduled sample and observation fulfilling any of the exclusion criteria will be excluded from summary statistics.

19.1. PHARMACOKINETIC CONCENTRATIONS

Individual PK blood sample collection times, derived sampling time deviations, and plasma concentrations of Debio 1143 and Debio 1143-MET1 and serum concentrations of nivolumab will be listed and figures will be presented for Cycle 1 Day 1. Time deviations will be calculated in reference to Debio 1143 administration or nivolumab infusion as specified in Table 8-1, Table 8-2, and Table 8-3 of protocol and taking into account the windows of tolerance specified in Table 8-5 of protocol.

Time deviations (actual sampling time outside the windows of tolerance specified in Table 8-5 of protocol) will be considered only relevant and a reason for data exclusion from PK analysis in case of pre-dose concentrations. All other post-dose time deviations will be considered not relevant and therefore concentrations will always be included in the PK analysis.

Should ADA samples be analyzed for serum ADA entities, results for nivolumab ADA will be listed, and ADA concentrations will be summarized only for ADA positive samples.

For each analyte, concentrations will be summarized using descriptive statistics (described in Section 7.6) by cycle, study day and scheduled time. In addition, the summaries for nivolumab concentrations will be stratified by Nivolumab regimen (240 mg or 480 mg) as applicable and summaries for Debio concentrations will be stratified by Debio regimen (150 mg or 200 mg).

Concentrations that are missing will be omitted from the calculation of descriptive statistics.

To derive PK parameters and for summary statistics (except for calculations involving logarithmic transformations), concentrations reported as BLQ will be considered as 0 when they occur before the first quantifiable concentration. BLQ concentrations occurring after the first quantifiable concentration will be set to 1/2 LOQ.

For summary statistics where calculation involves logarithmic transformations (including geometric mean calculation), plasma levels BLQ will be set to 1/2 LOQ.

Document: T:\sas\Debiopharm\Debio_1143\CZA60507\Biostatistics\Documentation\SAP\SAP Text\V5

Author: XXXXXXXXXX Version Number: 5.0
Version Date: 19APR2022

Template No.: CS_TP_BS016 Revision 5
Effective Date: 01Apr2018

Reference: CS_WI_BS005

Considering limited data and sample collections in patients, samples collected outside of protocol specified time windows will still be included in the summaries; except, pre-dose Debio 1143 (and Debio 1143-MET1) and nivolumab samples collected after administration of the respective drug will be excluded from the summaries.

For each analyte, figures of geometric mean concentrations ± geometric standard deviations on log10/linear scales will be presented. By-patient plots of individual concentration-time profiles log10/linear scales will also be presented.

19.2. PHARMACOKINETIC PARAMETERS

The PK parameters for Debio 1143, Debio 1143-MET1, and nivolumab in Part A and Part B will be calculated by noncompartmental method described below. If deemed appropriate, a population PK approach may be used and will be reported separately.

The actual elapsed time from Debio 1143 dose administration will be used for Debio 1143 and Debio 1143-MET1 analyses, and the actual elapsed time from the start of Nivolumab infusion will be used for Nivolumab analysis.

The PK calculated using available data include:

Debio 1143 and Debio 1143-MET1:		Part A	Part B
C_{max} (ng/mL)	Maximum concentration in plasma obtained directly from the observed concentration versus time data.	Cycle 1 day 1, day 8, day 15 and day 22 Cycle 3 day 1 and day 15 Cycle 6 day 1	Cycle 1 day 1, day 8, day 15 and day 22 Cycle 3 day 1 and day 15 Cycle 6 day 1
C_{max} (µmol/L)	C_{max} (ng/mL) transformed in molar units according to analyte molecular weight*	Cycle 1 day 1, day 8, day 15 and day 22 Cycle 3 day 1 and day 15 Cycle 6 day 1	Cycle 1 day 1, day 8, day 15 and day 22 Cycle 3 day 1 and day 15 Cycle 6 day 1
t_{max} (h)	Time of maximum concentration, obtained directly from the observed concentration versus time data.	Cycle 1 day 1, day 8, day 15 and day 22 Cycle 3 day 1 and day 15 Cycle 6 day 1	Cycle 1 day 1, day 8, day 15 and day 22 Cycle 3 day 1 and day 15 Cycle 6 day 1
$AUC_{(0-4h)}$ (ng·h/mL)	Area under the concentration-time curve in plasma from zero (pre-dose) to the 4-hour post-dose time point.	Cycle 1 day 1, day 8, day 15 and day 22 Cycle 3 day 1 and day 15	Cycle 1 day 1 and day 22 Cycle 3 day 1

Document: T:\sas\Debiopharm\Debio_1143\CZA60507\Biostatistics\Documentation\SAP\SAP Text\V5

Author: [REDACTED] Version Number: 5.0
Version Date: 19APR2022

Template No.: CS_TP_BS016 Revision 5
Effective Date: 01Apr2018

Reference: CS_WI_BS005

Copyright © 2009, 2010, 2012, 2016, 2018 IQVIA. All rights reserved. The contents of this document are confidential and proprietary to IQVIA Holdings Inc. and its subsidiaries. Unauthorized use, disclosure or reproduction is strictly prohibited.

Debio 1143 and Debio 1143-MET1:		Part A	Part B
AUC _(0-4h) (h·µmol/L)	AUC _(0-4h) (ng·h/mL) transformed in molar units according to analyte molecular weight*	Cycle 1 day 1, day 8, day 15 and day 22 Cycle 3 day 1 and day 15	Cycle 1 day 1 and day 22 Cycle 3 day 1
AUC _(0-8h) (ng·h/mL)	Area under the concentration-time curve in plasma from zero (pre-dose) to the 8-hour post-dose time point.	Cycle 1 day 1, day 8 and day 15 Cycle 3 day 1 and day 15	
AUC _(0-8h) (h·µmol/L)	AUC _(0-8h) (ng·h/mL) transformed in molar units according to analyte molecular weight*	Cycle 1 day 1, day 8 and day 15 Cycle 3 day 1 and day 15	
C _{trough} (ng/mL)	Minimal concentration in plasma before next dose obtained directly from the observed concentrations versus time	Cycle 1 day 3, day 8, day 17 and day 22 Cycle 3 day 3 and day 17	Cycle 1 day 8 and day 22
C _{trough} (µmol/L)	C _{trough} (ng/mL) transformed in molar units according to analyte molecular weight*	Cycle 1 day 3, day 8, day 17 and day 22 Cycle 3 day 3 and day 17	Cycle 1 day 8 and day 22
MR_AUC _(0-4h)	AUC _(0-4h) Metabolic ratio: Ratio of Debio 1143-MET1 AUC _(0-4h) /Debio 1143 AUC _(0-4h) , calculated as ratio for molar units	Cycle 1 day 1, day 8, day 15 and day 22 Cycle 3 day 1 and day 15	Cycle 1 day 1 and day 22 Cycle 3 day 1
MR_AUC _(0-8h)	AUC _(0-8h) Metabolic ratio: Ratio of Debio 1143-MET1 AUC _(0-8h) /Debio 1143 AUC _(0-8h) , calculated as ratio for molar units	Cycle 1 day 1, day 8 and day 15 Cycle 3 day 1 and day 15	

Document: T:\sas\Debiopharm\Debio_1143\CZA60507\Biostatistics\Documentation\SAP\SAP Text\V5

Author: ██████████

Version Number:

5.0

Version Date:

19APR2022

Template No.: CS_TP_BS016 Revision 5

Reference: CS_WI_BS005

Effective Date: 01Apr2018

Copyright © 2009, 2010, 2012, 2016, 2018 IQVIA. All rights reserved. The contents of this document are confidential and proprietary to IQVIA Holdings Inc. and its subsidiaries. Unauthorized use, disclosure or reproduction is strictly prohibited.

Debio 1143 and Debio 1143-MET1:		Part A	Part B
MR_C _{max}	C _{max} Metabolic ratio: Ratio of Debio 1143-MET1 C _{max} /Debio 1143 C _{max} , calculated as ratio for molar units	Cycle 1 day 1, day 8, day 15 and day 22 Cycle 3 day 1 and day 15 Cycle 6 day 1	Cycle 1 day 1, day 8, day 15 and day 22 Cycle 3 day 1 and day 15 Cycle 6 day 1

Document: T:\sas\Debiopharm\Debio_1143\CZA60507\Biostatistics\Documentation\SAP\SAP Text\5

Author: ██████████

Version Number:

5.0

Version Date:

19APR2022

Template No.: CS_TP_BS016 Revision 5

Reference: CS_WI_BS005

Effective Date: 01Apr2018

Copyright © 2009, 2010, 2012, 2016, 2018 IQVIA. All rights reserved. The contents of this document are confidential and proprietary to IQVIA Holdings Inc. and its subsidiaries. Unauthorized use, disclosure or reproduction is strictly prohibited.

Nivolumab:		Part A	Part B
C_{trough} (ng/mL)	Minimal concentration in serum before next dose obtained directly from the observed concentrations versus time	Cycle 1 day 15 Cycle 3 day 1 and day 15 (only those with 240 mg dose) Cycle 6 day 1	Cycle 1 day 15 Cycle 3 day 1 and day 15 (only those with 240 mg dose) Cycle 6 day 1
AUC_{tau} (ng·h/mL)	Area under the concentration-time curve in plasma from zero (pre-dose) to end of the dosing interval of 15 days	Cycle 1 day 1 (from day 1 pre-dose to pre-dose day 15) Cycle 3 day 1 (from day 1 pre-dose to day 15 (only those with 240 mg dose)	Cycle 1 day 1 (from day 1 pre-dose to pre-dose day 15)
AUC_{inf} (ng·h/mL)	Area under the concentration-time curve in plasma from time of dosing extrapolated to infinity	Cycle 1 day 1 and day 15	
C_{ss} (ng/mL)	Concentration at steady-state, concentration observed at the end of nivolumab infusion	Cycle 1 day 1 and day 15 Cycle 3 day 1 and day 15 (only those with 240 mg dose)	Cycle 1 day 1 and day 15 Cycle 3 day 1 and day 15 (only those with 240 mg dose)
CL (L/h)	Clearance calculated as Rate of nivolumab infusion/ C_{ss}	Cycle 1 day 1 and day 15 Cycle 3 day 1 and day 15 (only those with 240 mg dose)	Cycle 1 day 1 and day 15 Cycle 3 day 1 and day 15 (only those with 240 mg dose)

*Debio 1143 molecular weight: 561.71 g/mol; Debio 1143-MET1 molecular weight: 476.61 g/mol

The following PK parameters for Nivolumab will be listed only as supporting information for AUC_{inf} , but will not be summarized:

λ_z Apparent terminal rate constant (1/h), determined by linear regression of the terminal points of the log-linear concentration-time curve. Visual assessment will be used to identify the terminal linear phase of the concentration-time profile. A minimum of 3 data points will be used for determination.

Document: T:\sas\Debiopharm\Debio_1143\CZA60507\Biostatistics\Documentation\SAP\SAP Text\V5

Author: [REDACTED] Version Number: 5.0
Version Date: 19APR2022

Template No.: CS_TP_BS016 Revision 5
Effective Date: 01Apr2018

Reference: CS_WI_BS005

Copyright © 2009, 2010, 2012, 2016, 2018 IQVIA. All rights reserved. The contents of this document are confidential and proprietary to IQVIA Holdings Inc. and its subsidiaries. Unauthorized use, disclosure or reproduction is strictly prohibited.

$t_{1/2}$, Interval	The time interval (h) of the log-linear regression to determine λ_z
$t_{1/2}$, N	Number of data points included in the log-linear regression analysis to determine λ_z .
Rsq	Goodness of fit statistic for calculation of λ_z (Regression coefficient).
%AUC _{ex}	Percentage of AUC _(0-inf) obtained by extrapolation, calculated as $[(C_{last}/\lambda_z)/AUC_{(0-inf)} \times 100]$.

The AUCs for Debio 1143, Debio 1143-MET1, and Nivolumab will be calculated using linear up/log down trapezoidal summation.

For Nivolumab AUC_{inf}, if either or both of the following criteria are not met, the corresponding AUC_{inf} value will be listed only but excluded from the summary:

- Rsq (in the calculation of λ_z) > 0.85
- %AUC_{ex} < 15.0%

For each analyte, individual PK parameters will be listed and summarized using descriptive statistics (described in Section 7.6) by cycle and study day. In Part A, the summaries will be presented for each dose level and overall. In Part B, the summaries will be presented for each cohort and overall. In addition, the summaries for nivolumab concentrations will be stratified by Nivolumab regimen (240 mg or 480 mg) as applicable.

